 18. significant abnormality in clinical evaluations and/or laboratory tests (physical examination, vital signs, haematology, clinical chemistry, clinically relevant impaired renal function, defined as serum creatinine levels ≥ 2.0 x upper limit of normal, ECG) endangering the safe participation of the patient in the study at the Screening Visit (Visit 1) and during the study;
 19. participated in another investigational, interventional trial within 30 days prior to the Screening Visit (Visit 1);
 20. in the opinion of the Investigator not suitable for inclusion for whatever reason.
-

Outcome measures:

Primary Efficacy Variable:

Mean annual pulmonary exacerbation rate.

Secondary Efficacy Variables:

- CCI [REDACTED]
- [REDACTED]
- [REDACTED]
- [REDACTED]
- [REDACTED]
- [REDACTED]
- [REDACTED]
- [REDACTED]

Safety Variables:

- incidence of treatment emergent adverse events (TEAEs);
 - absolute changes in percent-predicted FEV₁ from baseline to each post-baseline visit;
 - number of subjects experiencing bronchospasm clinically or spirometrically determined following IMP administration;
 - CCI [REDACTED] as determined by *in-vitro* CCI [REDACTED] from Screening/Randomisation (Visit 1/Visit 2) to Visits 3, 5 and end of treatment (Visit 7) as well as on CCI [REDACTED] from Exacerbation Visits and clinic visits due to pneumonia;
-

-
- from Screening (Visit 1) to End of Treatment (Visit 7);
 - haematology, clinical chemistry and renal function tests;
 - physical examination and vital signs data;
 - 12-lead electrocardiogram.

Statistical Analysis

Primary analyses will be performed on the modified intention-to-treat (mITT) population with exclusions from the ITT defined and justified in the Statistical Analysis Plan (SAP). A supportive analysis will be conducted using a per-protocol (PP) population excluding subjects with major protocol deviations.

Annual pulmonary exacerbation rates will be compared between treatment groups using a Poisson regression model allowing for over-dispersion and also considering pooled site, use of stable concomitant therapy with oral macrolides and pulmonary exacerbation frequency in the 12 months preceding Visit 2 as covariates.

The primary analyses detailed above will be a comparison of colistimethate sodium against placebo at the end of the 12-month, double-blind phase. Full details will be provided in the SAP.

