18.4.2. EFFICACY DATA

The primary analysis will be performed on the mITT population. Analyses conducted using the PP will be considered supportive.

Primary Endpoint

In order to investigate whether the use of inhaled colistimethate sodium reduces the frequency of pulmonary exacerbations compared to placebo in subjects with NCFB chronically infected with *P. aeruginosa*, the following hypothesis will be tested:

- Null hypothesis A: there is no difference between inhaled colistimethate sodium and placebo as regards the effect on the pulmonary exacerbation rate against Alternative hypothesis A: inhaled colistimethate sodium reduces the pulmonary exacerbation rate.

The null hypothesis must be rejected for the efficacy of inhaled colistimethate sodium to be considered demonstrated.

A CCI analysis will be conducted using an alternative definition of NCFB pulmonary exacerbation. The re-classification of exacerbations will be conducted in a blinded fashion (before database lock). The alternative definition of pulmonary exacerbations used will be deterioration in three or more of the following key symptoms for at least 48 hours:

- Cough

Mean Annual Pulmonary Exacerbation Rate

The number of NCFB pulmonary exacerbations during the treatment period will be analysed using a Poisson regression model allowing for over-dispersion including treatment, pooled sites and use of stable concomitant therapy with oral macrolides as fixed effects and log-time on trial as an offset.

The number and the percentage of subjects with NCFB pulmonary exacerbations, the number of pulmonary exacerbations and the total follow-up time in years will be summarised by treatment group. The adjusted yearly mean exacerbation rates in each treatment group and the adjusted rate ratio with their 95% CIs will be estimated by the model.

For the analysis, 2 pulmonary exacerbations will be considered as a single episode in cases where the second exacerbation starts less than 14 days after the end of the antibiotic therapy (oral or intravenous) for the first pulmonary exacerbation.

If the null hypothesis will be rejected, additional investigation of proportionality of the hazard will be implemented in a secondary analysis. Additional details on the analysis will be provided in the SAP.

A corresponding two-sided p-value of <0.05 will be considered statistically significant.

Secondary Endpoints

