In order to investigate whether the use of inhaled colistimethate sodium reduces the frequency of pulmonary exacerbations compared to placebo in subjects with NCFB chronically infected with *P. aeruginosa*, the following hypothesis will be tested:

- Null hypothesis: there is no difference between inhaled colistimethate sodium and placebo as regards the effect on the pulmonary exacerbation rate

CONFIDENTIAL

Sponsor:	Zambon S.p.A.	Protocol Number:	Z7224L01
----------	---------------	------------------	----------

- Alternative hypothesis: inhaled colistimethate sodium reduces the pulmonary exacerbation rate in favour of inhaled colistimethate sodium compared to placebo.

The null hypothesis must be rejected for the efficacy of inhaled colistimethate sodium to be considered demonstrated.

The number and the percentage of subjects with NCFB pulmonary exacerbations, the number of NCFB pulmonary exacerbations and the total follow-up time in years, as defined in [Section 4.1.7](#), will be summarised by treatment group.

The number of NCFB pulmonary exacerbations during the treatment period will be analysed using a negative binomial model including treatment, pooled site, i.e. country, as detailed in [Section 4.9.1](#), and use of stable concomitant therapy with oral macrolides as fixed effects and log-time on treatment as an offset. If there is a significant p-value ($p < 0.05$) observed for the country covariate in this primary analysis then the number of NCFB pulmonary exacerbations during the treatment period will also be analysed using a negative binomial model for each country separately with use of stable concomitant therapy with oral macrolides as a fixed effect and log-time on treatment as an offset.

The adjusted mean annual NCFB pulmonary exacerbation rates in each treatment group and the adjusted rate ratio with their 95% CIs will be estimated by the model. OBSMARGINS option will be used for the estimates. The number of subjects considered in the model will be provided by treatment group. An adjusted rate ratio < 1 will indicate that colistimethate sodium decreases the rate of pulmonary exacerbations compared to placebo. A two-sided Wald chi-square test p-value of < 0.05 will be considered statistically significant. P-values of the effects based on Wald chi-square test will also be presented.

The log-time on treatment in years will be calculated using the following formula:

- $\text{Log-time on treatment} = \ln(\text{Follow-up time})$.

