4.7.4.3 CCI Analysis on Adherent Subjects

The primary analysis will also be repeated considering the subgroup of mITT subjects who were considered adherent, i.e. had an adherence of at least 80%.

4.7.4.4 Further Investigation: Number of Pulmonary Exacerbations in the 12 Months Prior to Study Entry

To further investigate any possible factor that might affect the mean annual NCFB pulmonary exacerbation rate, an exploratory negative binomial model will be fitted for the mITT population considering as an extra covariate the number of NCFB pulmonary exacerbations requiring oral or intravenous antibiotics in the 12 months prior to study entry.

4.7.4.5 Further Investigation: Stratified Analysis by Number of Pulmonary Exacerbation Requiring Oral or Intravenous Antibiotics in the 12 Months Prior to Study Entry

The number of NCFB pulmonary exacerbations requiring oral antibiotics in the last 12 months and the number of NCFB pulmonary exacerbations requiring intravenous antibiotics in the last 12 months prior to study entry, as collected in the eCRF Screening folder on the Non-CF Bronchiectasis History form, will be summed.

Analysis will be performed with the same criteria and methods as described for the primary efficacy model. If a subject has no data regarding the number of NCFB pulmonary exacerbations requiring oral and/or intravenous antibiotics in the last 12 months prior to study entry the subject will be excluded from the analysis.

A stratified analysis will also be performed classifying subjects according to the number of pulmonary exacerbations requiring oral or intravenous antibiotics in the 12 months prior to study entry, as reported in [Section 4.1.5](#).

4.7.4.6 Further Investigation: Stratified Analysis by Previous Usage of Colistimethate Sodium/Colistin

A stratified analysis will also be performed by previous usage of colistimethate sodium/colistin (as collected on the Non-CF Bronchiectasis History eCRF form) as reported in [Section 4.1.5](#).

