4.9 Adjustment for Covariates

The adjusted mean annual NCFB pulmonary exacerbation rate will be estimated by a negative binomial model including treatment, use of stable concomitant therapy with oral macrolides (e.g. azithromycin or erythromycin or clarithromycin: Yes/No) and pooled site, i.e. country, as detailed in Section 4.9.1, as fixed effects and log-time on treatment as an offset. An exploratory model will also be fitted considering the number of NCFB pulmonary exacerbations requiring oral/intravenous antibiotics in the last 12 months prior to study entry. The non-parametric ANCOVA model on ordered score for number of pulmonary exacerbations and on the annualised number of pulmonary CCI will include the same covariates.

The Cox proportional hazard regression model for CCI will include use of stable concomitant therapy with oral macrolides (e.g. azithromycin or erythromycin or clarithromycin: Yes/No) and pooled site, i.e. country, as covariates.

In the analysis of CCI total score and CCI domain scores, a linear mixed model for repeated measures will be applied. This will include treatment, visit, treatment-by-visit interaction, use of stable concomitant therapy with oral macrolides (e.g. azithromycin or erythromycin or clarithromycin: Yes/No) and pooled site, i.e. country, as fixed effects and baseline value as covariate.

The CCI will be analysed by means of an ANCOVA model including treatment, pooled site, i.e. country, and use of stable concomitant therapy with oral macrolides

CONFIDENTIAL

Sponsor:	Zambon S.p.A.	Protocol Number:	Z7224L01
----------	---------------	------------------	----------

(azithromycin or erythromycin or clarithromycin: Yes/No) as fixed effects and baseline value as covariate.

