4.13 Changes in Conduct or Planned Analyses from the Protocol

Sections 2.2, 4.4.11, 4.7.5 and 4.7.6.3: The protocol incorrectly referred to the units for the determination of CCI [REDACTED] which have been reported as CCI [REDACTED] by the central laboratory.

Section 3.9: The rationale and results for a reassessment of the original sample size calculation are provided to explain the reduced target sample size and associated levels of power.

Section 4.7.4: The protocol states that the Negative Binomial Model will consider the log-time on study as offset. However, as specified in Section 4.1.7, NCFB Pulmonary Exacerbations analyses focus on the treatment period so log-time on treatment will be considered.

Section 4.7.6.1: The protocol states that CCI [REDACTED] = CCI [REDACTED]. For time-to-event endpoints, generally the + 1 is not included because this overestimates the time by 1 day for every event, therefore "+ 1" has been deleted.

Section 4.7.6.4: The protocol states that any episodes of pneumonia will be considered as severe pulmonary exacerbations. Any reported episodes of pneumonia which do not require intravenous antibiotics and/or hospitalisation will be data queried to amend the Preferred Term. However, any pulmonary exacerbation on the Pulmonary Exacerbation form of the eCRF that is linked to an adverse event with a Preferred Term of 'Pneumonia' but does not have any CCI [REDACTED] or CCI [REDACTED] will be assumed to be a severe NCFB pulmonary exacerbation.

Section 4.7.6.5: The protocol states that the CCI [REDACTED] total score will be computed and analysed. However, as recommended in the Manual Scoring Instructions CCI [REDACTED] only the CCI [REDACTED] domain scores will be presented and analysed.

There have been no other changes in analyses from those defined in the protocol.

CONFIDENTIAL

Sponsor:	Zambon S.p.A.	Protocol Number:	Z7224L01
----------	---------------	------------------	----------

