- EoT should be replaced by the last time (in days) to event >270 days (if any);

- **Tables that require Cox proportional hazards model and 95% CIs of hazard ratios between treatments:**

*PROC PHREG data=dset;
CLASS treatment psite med;
MODEL time*event(1) = treatment psite med / ties=exact;
HAZARDRATIO 'Col. Sodium vs Placebo' treatment / cl=both;
BY byvar; (optional)
WHERE wherever; (optional)
RUN;*

Notes:

- Psite represents the pooled site, i.e. country, as detailed in [Section 4.9.1](#);
- Med represents use of stable concomitant therapy with oral macrolides (e.g. azithromycin or erythromycin or clarithromycin) (Yes/No);
- Time represents the time to event or time to censoring;
- Event represents the censoring indicator (1 = censored);
- If the option ties=exact requires a considerable amount of computer resources, the Efron approximation will be used (*ties=efron*).
- Treatment order: 1= Colistimethate Sodium, 2= Placebo.

CONFIDENTIAL

Sponsor:	Zambon S.p.A.	Protocol Number:	Z7224L01
----------	---------------	------------------	----------

- **Tables that require negative binomial modelling, including 95% CIs of treatment ratios:**

```
PROC GENMOD data = dset;
  CLASS treatment psite med;
  MODEL count = treatment psite med / offset=log_years link=log dist=negbin wald
  type3;
  ESTIMATE 'Col. Sodium / Placebo' treatment 1 -1 / exp;
  lsmeans treatment / ilink cl diff exp om;
  BY byvar; (optional)
  WHERE wherever; (optional)
RUN;
```

Notes:

- Psite represents the pooled site, i.e. country, as detailed in [Section 4.9.1](#);
- Med represents use of stable concomitant therapy with oral macrolides (e.g. azithromycin or erythromycin or clarithromycin) (Yes/No);
- Count represents the total number of exacerbations for each patient;
- log_years represents the logarithm of the follow-up time in years;
- Treatment order: 1= Colistimethate Sodium, 2= Placebo.

- **Tables that require linear mixed model for repeated measures and 95% CIs of differences between treatments:**

```
PROC MIXED data = dset;
  CLASS treatment visit psite med sub;
  MODEL change = treatment visit treatment*visit psite med baseline/ s ddfm=kr;
  REPEATED visit / subject=sub type=un r;
  LSMEANS treatment treatment*visit / om at means cl slice=visit;
  LSMESTIMATE treatment
  'Col. Sodium / Placebo' 1 -1 / cl;
  LSMESTIMATE treatment*visit
  'Col. Sodium / Placebo: Visit 4' 1 0 0 0 -1 0 0 0,
  'Col. Sodium / Placebo: Visit 5' 0 1 0 0 0 -1 0 0,

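### The protocol Summary adjusts the primary rate model for prior-year exacerbations, section 18.4.2 and the SAP do not, and SAP 4.13 records neither that choice nor the change from over-dispersed Poisson to negative binomial

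*SAP*

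**What the plan says.** **Protocol, Summary (Statistical Analysis).** Annual rates are compared by Poisson regression with allowance for over-dispersion. Besides pooled site and macrolide use, the model takes "pulmonary exacerbation frequency in the 12 months preceding Visit 2 as covariates".

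**Protocol 18.4.2.** The count "will be analysed using a Poisson regression model allowing for over-dispersion including treatment, pooled sites and use of stable concomitant therapy with oral macrolides". Prior exacerbations are not in the list.

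**SAP 4.7.4.** The model is negative binomial, with treatment, country "and use of stable concomitant therapy with oral macrolides as fixed effects and log-time on treatment as an offset". The code in SAP 4.14 agrees: "MODEL count = treatment psite med / offset=log_years link=log dist=negbin wald".

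**SAP 4.9 and 4.7.4.4.** Prior exacerbations appear only outside the primary model: "An exploratory model will also be fitted considering the number of NCFB pulmonary exacerbations requiring oral/intravenous antibiotics in the last 12 months". The result goes to Table 14.2.1.1.6. SAP 4.7.4.5 adds an analysis stratified by the prior count.

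**SAP 4.13.** On the form of the primary model, the only entry concerns the offset: "The protocol states that the Negative Binomial Model will consider the log-time on study as offset". The section closes: "There have been no other changes in analyses from those defined in the protocol".

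**Prior-exacerbation levels.** SAP 4.1.5 and 4.7.4.5 sum events treated with oral and with intravenous antibiotics. SAP 4.1.5 and addendum 6.1.2 use levels 1, 2 and >2. Inclusion criterion 4 (protocol 7.2.1) also admits subjects on exacerbations treated with inhaled antibiotics.

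**The concern.** Someone reading the Summary expects one covariate more than was fitted, and a different model family. The section that should explain such differences is silent on the first, misdescribes the second and then denies that anything else changed. This is the primary endpoint, and the model will be examined closely: addendum 6.1.1 reports significance under missing-at-random imputation and its loss under copy-reference imputation (the note to file has that table rerun to correct double counting).

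There is also a possible loss of precision. The prior-year count is collected on every subject's history form and the Summary names it. If it is prognostic, adjusting for it narrows the interval at no cost in data.

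The linked gap is in the subgroup and interaction tables, which the addendum uses to check internal consistency. A subject who entered on inhaled-treated events alone has a count of 0 and fits no level, or is excluded if the fields are blank.

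**Working it through.** **1. The sources side by side**

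| Source | Model | Terms besides treatment | Offset |
|---|---|---|---|
| Protocol Summary | Over-dispersed Poisson | Pooled site, macrolide use, prior-12-month exacerbations | Not stated |
| Protocol 18.4.2 | Over-dispersed Poisson | Pooled site, macrolide use | Log-time on trial |
| SAP 4.7.4, 4.9, 4.14 | Negative binomial | Country, macrolide use | Log-time on treatment |
| SAP 4.13 (change record) | Says the protocol named negative binomial | No entry | Change recorded |

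The covariate conflict starts inside the protocol. The family change lies between the protocol and the SAP.

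**2. Reproducing the plan's figure.** Inputs from SAP 3.9: rates 1.2701 and 0.8256 per year, over-dispersion k = 0.273, 90% power. The protocol gives two-sided 0.05. With n per arm and t years of exposure,

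Var(log RR) = [1/(1.2701t) + 1/(0.8256t) + 2k] / n.

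At t = 1 the bracket is 0.787 + 1.211 + 0.546 = 2.545. Then n = (1.960 + 1.282)² × 2.545 / (ln 0.650)² = 10.507 × 2.545 / 0.1855 = 144.1, so 145 per arm, as the SAP states.

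**3. Implied exposure.** Setting n = 188 (the dropout-adjusted figure in SAP 3.9) at 90% power gives t = 0.7206 year. With 377 randomised, 188.5 per arm, the formula gives 90.1% power.

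**4. Effect of the covariate.** Let it remove a share of k. No document gives this share; 20 to 40% is an assumption, and 100% is the upper limit within this formula.

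| Share of k removed | Variance ratio | CI width ratio | Power | Worth in subjects |
|---|---|---|---|---|
| 0% | 1 | 1 | 90.1% | 0 |
| 20% | 0.967 | 0.983 | 91.0% | 13 |
| 40% | 0.934 | 0.967 | 91.9% | 27 |
| 100% | 0.836 | 0.914 | 94.4% | 74 |

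**5. Simulation with country terms.** Assumptions: 377 subjects, 15 uneven countries (64 down to 2 subjects), 30% macrolide users, mean exposure about 0.72 year, prior levels split 25/45/30%. Adding the prior count as a linear term moved power from 89.2% to 90.1% (20% share) and from 89.2% to 91.1% (40% share). With a non-prognostic count it went from 89.5% to 89.6%. Type I error was 5.9 to 6.0% without the covariate and 5.8 to 6.3% with it (simulation SE 0.3), so validity does not turn on it.

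**6. Model family.** In the same setting, Poisson with an estimated scale gave 88.9% power against 89.2% for negative binomial, and type I error 5.8% against 5.9 to 6.0%. A simpler simulation (no covariates, 170 per arm, one full year, k = 0.337 assumed) gave 90.5% against 90.6% power at a 35% reduction, and type I error 5.4% against 5.3%.

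**7. Who can be affected by the level gap.** The summary of changes adds inhaled-treated events to criterion 4; its CRO change matches v7.0, dated 22 October 2019. SAP 3.9 has 342 randomised subjects in the data at 15 January 2020 and recruitment closed at 377, so 377 − 342 = 35 came later. Some of the 342 may also have entered after v7.0, so 35 is not a strict ceiling, but the route was open only near the end.

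**The case against.** The SAP can be defended on covariates. It matches protocol 18.4.2, the detailed statistical section, and the Summary defers full details to the SAP. Prior exacerbations are not dropped: there is a prespecified adjusted model and a stratified analysis. All of this stands. It makes the covariate question an unexplained resolution of a protocol conflict, not a departure from the statistical section.

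On the model family, protocol 18.3 simulated negative binomial counts, and over-dispersed Poisson can be read loosely to include that model. This softens the point, but 18.3 still names Poisson regression as the analysis, and 4.13 reports wording that the protocol does not contain.

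The precision loss is conditional. It rests on an assumed share, and the Summary's own model is Poisson with the covariate, so the small family variance ratio (1.012 to 1.019) would offset part of the 3.3% variance gain at a 20% share.

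A reader might infer that the covariate was left out after results were seen. The documents do not support this: protocol v7.0 section 18.4.2 already omits it, and SAP v2.0 writes of blind review and database lock as still to come. A reader might also make something of the two 12-month windows, before Visit 2 and before Screening. Screening lasts up to 30 days and criterion 4 bars exacerbations between Visits 1 and 2, so they differ by at most about 30 days at the far end.

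**Conclusion.** The point holds as a documentation fault on the primary endpoint, with a small and conditional cost in precision. The protocol contradicts itself on the prior-exacerbation covariate, the SAP settles the matter silently, and SAP 4.13 is wrong about the model family and incomplete.

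The primary test is valid: the SAP names one model, and simulated type I error is about the same either way. The family change is nearly neutral. The possible cost of omitting the covariate is about 1 to 2 points of power, resting on the assumed 20 to 40% share, with none if the count is not prognostic. A reader might infer a demonstrated loss, or that the primary analysis should now be replaced. Neither follows: no document gives the prognostic strength, and addendum 2.2 states that the database is locked and the study unblinded.

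The gap in the prior-exacerbation levels is real but secondary. It touches subgroup and interaction tables, not the primary model, and few subjects can be affected. Their exact number is not given.

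**What to change.** **What the plan should say.** Put the prior-12-month exacerbation count in the primary negative binomial model in SAP 4.7.4, 4.9 and the 4.14 code, as the Summary states, with the model without it as sensitivity. Bring the Summary and 18.4.2 into line.

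**What to do now.** Leave the prespecified primary result in place. Show the prespecified Table 14.2.1.1.6 beside it, and label any further adjusted run post hoc. Correct the change record, in SAP 4.13 or the report, with two entries: the conflict between the Summary and 18.4.2 and how it was resolved, and the change from over-dispersed Poisson to negative binomial.

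**Levels.** In SAP 4.1.5 and 4.7.4.5 and addendum 6.1.2, count inhaled-treated events if they were collected. Otherwise show subjects who entered on inhaled-treated events alone as a separate level.

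**Cost.** Disclosure needs no new run, since Table 14.2.1.1.6 is already planned. Made before unblinding, the full model change would have touched the primary and imputation code and about 10 tables that directly inherit the model; about 11 further country, subgroup and interaction tables are also built on it. The documents do not show a field for inhaled-treated events, so the recount may not be possible. The separate level requires only that these entrants can be identified.
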